8.2. Subject Exclusion Criteria

Subjects must meet none of the following exclusion criteria (where applicable) prior to first dose of BCX9930 on Day 1 or specified time below:

- 1. Known congenital deficiency of C1s, C1r, C1q, C2, C4. Known variants in complement Factor H, complement Factor I, C3, and complement Factor B or genomic rearrangements in the complement Factor-H-related proteins are not exclusionary
- 2. Receiving hemodialysis or peritoneal dialysis or anticipated to receive dialysis during the duration of this study.
- 3. History of hematopoietic cell transplant or solid organ transplant or anticipated candidate for transplantation during the study.
- 4. History of transfusion with blood or blood products, or plasmapheresis or plasma exchange, within 30 days prior to screening.
- 5. Myocardial infarction or cerebrovascular accident within 30 days prior to screening, or current and uncontrolled clinically significant cardiovascular or cerebrovascular condition, including unstable angina, severe congestive heart failure, unexplained syncope, arrhythmia, and critical aortic stenosis.
- 6. History of malignancy within 5 years prior to the screening visit, with the exception of adequately treated non-melanoma skin or superficial bladder cancer, curatively treated carcinoma in situ of the cervix, or other curatively treated solid tumor deemed by the investigator and medical monitor to be at low risk for recurrence.
- 7. Any clinical or pathological evidence of monoclonal gammopathy of unclear or renal significance, lupus or other systemic autoimmune disease, or other conditions (eg, infection-associated disease or associated with another systemic disease, anti-phospholipid antibody syndrome with significant clinical disease, immune complex glomerulonephritis, immunoglobulin A [IgA] vasculitis with nephritis [Henoch-Schönlein purpura] or morphologic features of secondary membranous nephropathy). Presence of C3 or C5 nephritic factors (eg, autoantibodies directed at C3 or C5 convertase), in the absence of known infection or other systemic disease, are not exclusionary for this study.
- 8. Treatment with azathioprine, canakinumab, cyclophosphamide, cyclosporine, eculizumab, everolimus, hydroxychloroquine, infliximab, sirolimus, ravulizumab, systemic corticosteroids (including budesonide), tacrolimus, or any other systemic immunosuppressive or immunomodulatory therapies (eg, complement inhibitors) within 90 days OR mycophenolate mofetil/mycophenolate sodium treatment within 60 days OR anti-CD20 antibody therapies (eg, rituximab) within 180 days prior to the screening visit.

- a. For subjects with C3G only, ongoing treatment with a stable dose of mycophenolate mofetil/mycophenolate sodium for at least 6 months prior to the Day 1 Visit is allowed
- 9. Treatment with renin inhibitors (eg, aliskiren) or sodium-glucose-cotransporter 2 (SGLT2) inhibitors within 60 days prior to Day 1.
- 10. Current participation in any other investigational drug study or participation in an investigational drug study within 30 days prior to the screening visit, or 5.5 half-lives of the investigational drug, whichever is longer.
- 11. Any of the following laboratory values at the screening visit: hemoglobin < 8.5 g/dL; total white blood cell (WBC) < 2.5×10^9 /L; absolute neutrophil count (ANC) < 1.0×10^9 /L; platelet count < 90×10^9 /L; ALT, AST, alkaline phosphatase (ALP), or total bilirubin > $1.5 \times ULN$; serum albumin < 1.5 g/dL; or INR > 1.4.
 - a. Subjects with Grade 1 elevated bilirubin due to Gilbert's syndrome are allowed to enroll. To document that a subject has Gilbert's syndrome, a diagnosis from the medical record must be provided, or the investigator may make a presumptive diagnosis of Gilbert's syndrome in subjects with unconjugated hyperbilirubinemia on repeated testing (at least 2 samples separated in time) who have ALT, AST, and ALP ≤ 1.5 × ULN, and a normal complete blood count.
- 12. Any laboratory parameter at screening that, in the judgment of the investigator, is clinically significant and would represent a safety concern.

Note: Enrollment of a subject with laboratory value(s) outside of the reference range may be permissible if the abnormality is documented by the investigator to not be of clinical significance, or is disease related, and does not pose a safety concern.

- 13. Clinically significant abnormal ECG prior to dosing at the Day 1 Visit.
- 14. Current use of a prohibited concomitant medication within 7 days prior to Day 1 as detailed in Section 9.2.
- 15. Active serious bacterial, viral, or fungal infection or any other serious infection, including suspected or confirmed severe acute respiratory syndrome coronavirus 2 [SARS-CoV-2] infection, within 14 days of screening. Dyspnea, vasculitic rash, and persistent fever or other symptoms consistent with multisystem inflammatory syndrome [MIS] are exclusionary in the setting of recent SARS-CoV-2 infection.
- 16. Positive serology for human immunodeficiency virus (HIV), or active infection with hepatitis B virus (HBV) or hepatitis C virus (HCV).
- 17. Positive test for drugs of abuse during screening, unless by prescription where legal.
- 18. Pregnant, planning to become pregnant, or breastfeeding.
- 19. Known or suspected hypersensitivity to BCX9930 or any of its formulation excipients as detailed in Section 10.1.
- 20. History of severe hypersensitivity to any medicinal product, which was associated with swelling, severe rash requiring treatment/hospitalization, or anaphylaxis.

21. Any clinically significant medical or psychiatric condition, including known or suspected substance abuse (including alcohol) that, in the opinion of the investigator or sponsor, would interfere with the subject's ability to participate in the study or increase the risk of participation for that subject.

9. TREATMENT OF SUBJECTS

9.1. Prior/Concomitant Medications

All medications will be documented beginning 30 days prior to the screening visit. All concomitant medication use, beginning with the screening visit and including all medications administered for the treatment of AEs, will be recorded.

Prior to enrollment, the investigator should review the subject's medication list for potentially nephrotoxic medications and consider, when medically feasible, whether these medications may be stopped or substituted with non- or less nephrotoxic medications. Caution should be exercised with the chronic use of non-steroidal anti-inflammatory drugs (NSAIDs) while taking BCX9930.

With the exception of any changes to nephrotoxic medications and prohibited and restricted medications detailed in Section 9.2, subjects should continue their normal medications. Dosing of medications that increase infection risk (eg, mycophenolate mofetil/mycophenolate sodium) should remain stable until at least the Week 52 visit unless taper or discontinuation needs to be done for safety reasons.

If any dose adjustments to the protocol-required stable, maximum tolerated dose of either an ACEi or ARB are needed for the treatment of a subject during the study or if it is discovered that the subject's ACEi or ARB dose has been changed, then the investigator (or qualified designee) should notify the medical monitor.

Prophylactic use of antibacterial and antiviral medications may be considered if clinically indicated and after discussion with the sponsor medical monitor (or designee), with consideration of the list of prohibited and restricted medications separate from this protocol (see Section 9.2).

Please refer to inclusion criterion 13 and Section 12.2.1 for vaccination requirements and recommendations.

9.2. Prohibited and Restricted Medications

All subjects should observe the prohibitions and restrictions on concomitant use described in Section 8.2, and in the following text for the appropriate window prior to screening or Day 1. In addition, all subjects must have discontinued all prohibited medications for a minimum of 7 days prior to Day 1 and have an agreed plan in place for monitoring any restricted medications that will be continued. Similarly, dose adjustments to restricted medications should be completed at least 7 days prior to Day 1.

All subjects in the study should refrain from taking the following prohibited medications from the screening visit through the safety FU visit:

• Any systemic immunosuppressive or immunomodulatory medications (eg, azathioprine, canakinumab, cyclophosphamide, cyclosporine, eculizumab,

everolimus, hydroxychloroquine, infliximab, sirolimus, ravulizumab, systemic corticosteroids, tacrolimus, anti-CD20 antibody therapies [eg, rituximab], or complement inhibitors other than study drug)

- Renin inhibitors (eg, aliskiren)
- SGLT2 inhibitors

Note: Up to 7 adults with C3G with at least 6 months of stable dosing with mycophenolate mofetil or mycophenolate sodium prior to the Day 1 Visit will be allowed to continue dosing throughout the study as described in Section 9.1.

The sponsor will provide a list separate from the protocol of prohibited and restricted medications for which there may be a drug interaction with BCX9930 based upon regulatory labeling for individual medications, regulatory guidances, peer-reviewed literature, and regularly updated drug interaction reference databases (eg, University of Washington School of Pharmacy Drug Interaction Database, PharmaPendium). The sponsor may modify this list of prohibited medications based upon available PK and safety data on concomitant medications, ongoing clinical findings, and continued review of labeling, regulatory guidances, literature, and reference databases. A memorandum of any such changes to this list will be provided to all clinical sites.

Phase 1 DDI studies may be conducted and resulted during the conduct of this study. Should the guidance for individual medications change, the use of currently prohibited medications may be subsequently allowed based upon the quantitative data generated in the DDI study. A summary and justification of the updated allowance/guidance will be provided to all clinical sites along with a revised list of prohibited medications.

During the study, the CYP enzymes and drug transporters of clinical concern may be modified based on drug interaction studies. Medications that potentially affect the metabolic pathways or transport of BCX9930 may also be added, pending availability of additional data.

Throughout the course of the study, investigators should inquire about newly initiated daily chronic use medications; the investigator should compare these medications to the prohibited medication list.

Similarly, subjects should be aware that there may be restricted medications in this study and should inform all treating physicians of their participation in this study and the possibility of potential interactions with BCX9930.

If any of these prohibited medications are determined to be needed for the treatment of a subject during the study or if it is discovered that the subject is already receiving a prohibited medication during study participation, then the investigator (or qualified designee) should contact the medical monitor. Investigators should contact the sponsor medical monitor for specific questions regarding prohibited and restricted medications as needed.

9.3. Treatment Compliance

The first dose of BCX9930 on Day 1 will occur in the clinic under supervision. All subsequent doses can be taken at home; subjects do not need to withhold any doses on clinic days or take a dose at the clinic, unless the clinic visit falls during the subject's normal time of dosing, or the subject is participating in the optional PK/PD substudy on a given visit. For subjects who are participating in the PK/PD substudy and are scheduled to have serial PK/PD collections on a clinic day, the morning dose of BCX9930 will need to be withheld until the scheduled visit. Subjects will be provided instructions for taking daily doses of study drug, including frequency and time of administration. Subjects will be instructed to maintain approximately the same approximate 12-hour dosing interval between study drug doses each day (eg, 8:00 AM and 8:00 PM).

It is anticipated that subject compliance with the BID dosing schedule for BCX9930 is important for the benefit of subjects and for success of this study. Investigators should remind participants who regularly miss doses about the importance of treatment compliance. Drug compliance will be recorded in the eCRF.

9.3.1. Missed Doses:

If the subject forgets to take the study drug at the correct time, the dose may be taken as late as 6 hours after the scheduled dose time. If more than 6 hours has passed, subjects should skip the missed dose entirely and take the next dose at the scheduled time. Regardless of whether the missed dose was made up, dosing should resume with the next dose taken at the scheduled time. For example, a subject who normally takes the BCX9930 doses at 8:00 AM/PM each day can take a missed morning dose as late as 2:00 PM with the evening dose administered on schedule

at 8:00 PM. A missed evening dose can be taken as late as 2:00 AM the next day, with the next dose taken on schedule at 8:00 AM.

9.4. Randomization and Blinding

This is an open-label, non-randomized study. No study treatments will be blinded or masked.

10. STUDY DRUG MATERIALS AND MANAGEMENT

10.1. BCX9930

BCX9930 is a small-molecule inhibitor of Factor D and will be provided as tablets for oral administration. The active ingredient is BCX9930 drug substance.

BCX9930 tablets contain the active ingredient blended with the excipients

Dosage forms include BCX9930 tablets of 100-, 200-, and 250-mg strength, which are all from a dose-proportional blend compressed into tablets of the desired weight.

Additional details of the chemical and physical characteristics of BCX9930 may be found in the IB for BCX9930 and investigational medication product (IMP) manual. Please note both IMP and study drug refer to BCX9930 in this protocol.

10.2. Description of Study Drug Packaging, Labelling, and Storage

The study drug will be packaged in the appropriate size bottle. Each bottle will be labeled with the information required per local law, which may include sponsor name, study protocol number, description of the contents, a statement regarding the investigational (clinical study) use of the study drug, and expiry date.

The bottles of BCX9930 tablets should be stored at 15°C to 25°C (59°F to 77°F).

10.3. Administration

Subjects who previously received 500 mg BID and remain on study treatment will be dose adjusted to 400 mg BID.

For newly enrolled subjects, BCX9930 will be initiated at a dose of 200 mg BID for the first 14 days and will be increased to 400 mg BID on Day 15 for the remainder of the up to 52-week treatment period. Subjects will be instructed to take the BCX9930 tablets orally twice daily at approximately the same times each day (ie, at intervals of approximately 12 hours), either with or without food. Adequate hydration should be maintained to support kidney function and prevent the formation of highly concentrated urine.

No additional study drug preparation is required. BCX9930 tablets will be taken from the provided bottles.

Subjects will be dispensed a sufficient number of bottles and BCX9930 tablets to cover the dosing period until the next study visit.

Drug dispensation will occur in clinic but may be delivered to subjects by other means (eg, traceable courier) if warranted due to extenuating circumstances (eg, COVID-19 restrictions) which will be determined individually for each site and/or subject taking into account applicable local law or regulation.

Subjects will be instructed to bring all bottles of study drug (both unused and used bottles) with them to all study visits at the investigative site (including any unscheduled visits, when possible). Drug accountability and treatment adherence will be reviewed at these visits.

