 - Decreased endocapillary hypercellularity, mesangial hypercellularity, active crescents (if present), glomerular leukocyte infiltration, fibrinoid necrosis, membranoproliferative glomerulonephritis pattern
 - Decreased acute tubular injury, interstitial inflammation, interstitial edema
 - Reduction in C3 glomerular staining
 - Reduction in the extent of deposits, clearing of deposits, or no additional active deposits as assessed by electron microscopy (EM)
 - No progression of chronic changes (ie, global, segmental glomerulosclerosis, tubular atrophy/interstitial fibrosis, arteriosclerosis)
- Number and proportion of subjects with a treatment-emergent adverse event(s)(TEAE)

- Number and proportion of subjects who discontinue due to a TEAE
- Number and proportion of subjects who experience a treatment-emergent serious adverse event (TESAE)
- Number and proportion of subjects who experience a Grade 3 or 4 TEAE based on Common Terminology Criteria for Adverse Events (CTCAE)
- Number and proportion of subjects who experience a CTCAE treatment-emergent Grade 3 or 4 laboratory abnormality

Exploratory Endpoints:

Study Design:

This is a Phase 2, open-label, multicenter, POC study to evaluate the safety, tolerability, and therapeutic potential of BCX9930, an oral Factor D inhibitor, administered for up to 52 weeks in adult (≥ 18 years old) subjects with C3G, IgAN, or PMN. After up to a 56-day screening qualification period, approximately 14 eligible subjects will be enrolled into each of three parallel study treatment cohorts and will receive BCX9930 200 mg twice daily (BID) for the first 14 days and 400 mg BID on Day 15 and for the remainder of the treatment period, up to a total duration of 52 weeks. Each cohort may be analyzed separately.

Methodology:

During the study, recruitment into each of the cohorts will be managed independently with a total of approximately 42 subjects enrolled into the study. For the C3G cohort only, up to 7 subjects with at least 6 months of treatment with a stable dosing regimen of mycophenolate mofetil/mycophenolate sodium prior to the Day 1 Visit will be allowed to enroll in the study.

The independent BCX9930 DMC will regularly review cumulative safety data from this study, as well as accumulating, long-term safety data across all BCX9930 studies in all indications.

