- 15. Active serious bacterial, viral, or fungal infection or any other serious infection, including suspected or confirmed severe acute respiratory syndrome coronavirus 2 [SARS-CoV-2] infection, within 14 days of screening. Dyspnea, vasculitic rash, and persistent fever or other symptoms consistent with multisystem inflammatory syndrome [MIS] are exclusionary in the setting of recent SARS-CoV-2 infection.

- 16. Positive serology for human immunodeficiency virus (HIV), or active infection with hepatitis B virus (HBV) or hepatitis C virus (HCV).
- 17. Positive test for drugs of abuse during screening, unless by prescription.
- 18. Pregnant, planning to become pregnant, or breastfeeding.
- 19. Known or suspected hypersensitivity to BCX9930 or any of its formulation excipients.
- 20. History of severe hypersensitivity to any medicinal product, which was associated with swelling, severe rash requiring treatment/hospitalization, or anaphylaxis.
- 21. Any clinically significant medical or psychiatric condition, including known or suspected substance abuse (including alcohol) that, in the opinion of the investigator or sponsor, would interfere with the subject's ability to participate in the study or increase the risk of participation for that subject.

Investigational Product, Dosage and Mode of Administration:

Subjects who previously received 500 mg BID and remain on study treatment will be dose adjusted to 400 mg BID. For all newly enrolled subjects, subjects will initially receive BCX9930 200 mg BID for the first 14 days of treatment before increasing the dose to 400 mg BID on Day 15 for the remainder of the treatment period. The appropriate quantity of BCX9930 tablets will be taken orally, twice a day, approximately 12 hours apart, without regard to food. Adequate hydration should be maintained to prevent the formation of highly concentrated urine.

Duration of Treatment:

Subjects will receive open-label BCX9930 for up to 52 weeks.

Reference Therapy, Dosage and Mode of Administration:

N/A

[figure not shown]
Criteria for Evaluation:

Safety: Safety will be evaluated by TEAEs, laboratory analyses (clinical chemistry, hematology, coagulation, urinalysis including microscopy), vital signs, ECGs, and physical examination findings. In addition, potential drug-induced liver injury, potential drug-induced kidney injury, and SARS-CoV-2 infection (asymptomatic and symptomatic) events, including non-serious events, may have enhanced data collection.

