7. INVESTIGATIONAL PLAN

7.1. Overall Study Design

This is a Phase 2, open-label, multicenter, POC study to evaluate the safety, tolerability, and therapeutic potential of BCX9930, an oral Factor D inhibitor, administered for up to 52 weeks in adult (≥ 18 years old) subjects with either C3G, IgAN, or PMN. After up to a 56-day screening

qualification period, approximately 14 eligible subjects will be enrolled into each of 3 parallel study treatment cohorts and will receive BCX9930 200 mg BID for the first 14 days and will increase to BCX9930 400 mg BID on Day 15 for the remainder of the treatment period.

During the study, recruitment into each of the cohorts will be managed independently with a total of approximately 42 subjects enrolled into the study. For the C3G cohort only, up to 7 subjects with at least 6 months of treatment with a stable dosing regimen of mycophenolate mofetil or mycophenolate sodium prior to the Day 1 Visit will be allowed to enroll in the study per Section 8.2. Sites will be notified when enrollment is complete for subjects with C3G receiving mycophenolate mofetil/mycophenolate sodium.

After providing written informed consent to participate in the study and confirming that all other study eligibility criteria have been met during screening, subjects will undergo a percutaneous needle biopsy of the kidney per local practice and guidelines. Renal biopsy images and details from the local pathology report will be reviewed by the central pathologist for confirmation of a protocol-defined diagnosis of C3G, IgAN, or PMN. The screening biopsy procedure may be waived with approval of the central pathologist and agreement with the medical monitor for any subject who has undergone a renal biopsy procedure as follows: within 3 months prior to screening for the C3G cohort, within 6 months prior to screening for the IgAN or PMN cohorts, provided that required materials are adequate for pathology evaluation per protocol procedures.

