7.3. Treatment Assignment

All eligible subjects will receive BCX9930 200 mg BID for the first 14 days and will increase to BCX9930 400 mg BID on Day 15 for the remainder of the treatment period; doses should be taken approximately 12 hours apart. The first dose of BCX9930 will be administered at the Day 1 Visit after completion of all baseline procedures and under supervision of clinic staff.

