11.3.3. Baseline Visit (Day 1)

For subjects participating in the PK/PD substudy, please refer to Table 2 and Table 4 for procedures and timings.

Before any study drug is administered, the following assessments will be completed:

• Administration of questionnaires:

- Review of inclusion and exclusion criteria and prohibited medications
- Review of medical and medication history
- Review of Disease Specific Medical History Form
- Weight and BMI

- 12-lead ECG (triplicate ECGs)
- Vital signs (blood pressure, temperature, and pulse rate)
- Complete physical examination
- Single void urine collection for urinalysis including microscopy and biomarkers
- A urine pregnancy test for female subjects of childbearing potential. A negative urine pregnancy result must be recorded in order for the subject to receive study drug.
- Blood collection for clinical chemistry, hematology, coagulation, and PD biomarkers
- Review concomitant medications and AEs
- Provide collection container with instructions and return of an intended 24-hour urine sample
- Study drug dispensing (via IRT)

Where possible, the questionnaires should be completed by the subject prior to other assessments to prevent influencing subject perceptions.

11.3.4. On-study Visits (Weeks 1, 2, 4, 8, 12, 16, 20, 24, 28, 32, 36, 40, 44, 48, and 52)

Subjects will return to the clinic during Week 1 (Day 8 ± 1 day), Week 2 (Day 15 ± 1 day), Week 4 (Day 29 ± 1 day), Week 8 (Day 57 ± 3 days), Week 12 (Day 85 ± 3 days), Week 16 (Day 113 ± 3 days), Week 20 (Day 141 ± 3 days), Week 24 (Day 169 ± 3 days) Week 28 (Day 197 ± 3 days), Week 32 (Day 225 ± 3 days), Week 36 (Day 253 ± 3 days), Week 40 (Day 281 ± 3 days), Week 44 (Day 309 ± 3 days), Week 48 (Day 337 ± 3 days), and Week 52 (Day 365 ± 3 days).

At the Week 24 Visit, the clinical benefit of BCX9930 treatment will be assessed by the investigator. Subjects who are assessed as deriving clinical benefit will continue treatment up to Week 52. Subjects who continue BCX9930 treatment will complete study visits and assessments through the Week 52 Visit.

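### The increase to 400 mg BID is fixed on Day 15, so unless a Week 2 result is back within about a day, the newest creatinine at the doubling is the Week 1 value, 6 to 8 days old

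*Protocol*

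**What the plan says.** The dosing rule is a calendar rule wherever it appears. Protocol 10.3 has treatment "initiated at a dose of 200 mg BID for the first 14 days and will be increased to 400 mg BID on Day 15". Section 7.3 says that all eligible subjects "will increase to BCX9930 400 mg BID on Day 15 for the remainder of the treatment period", and 7.1 and the synopsis agree ("200 mg twice daily (BID) for the first 14 days and 400 mg BID on Day 15"). None of these gives a window for the increase or a laboratory condition.

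Section 11.3.4 places the second on-treatment visit at "Week 2 (Day 15 ± 1 day", that is Day 14 to 16; Week 1 is Day 8 ± 1. Table 3 schedules chemistry at both visits and none between them. Table 6 lists serum creatinine in the chemistry panel. The first of the additional renal and hepatic checks is Week 3, Day 22 ± 1 (11.3.5).

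Under 12.11.5, samples at site visits generally use central laboratory kits. Local laboratories are allowed at the investigator's discretion, for instance when a faster result is needed. Table 3 shows neither drug dispensing nor an interactive response system entry at Week 2. Both occur on Day 1 and next at Week 4, so no scheduled supply step holds back the higher dose.

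Section 5.5.5 presents the lower target dose together with the two-week start at 200 mg BID as the way renal risk is expected to be reduced.

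**The concern.** The lead-in exposes the kidney to a lower dose before the full one. It is most useful if someone sees how the kidney responded to the lead-in before the dose doubles. With the increase on Day 15 and the second creatinine drawn within a day either side of it, that result will often arrive afterwards. A rise that begins on 200 mg BID after the Week 1 sample could then be recognised only once the subject is on 400 mg BID.

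The protocol treats this risk as real. Section 13.4.1 regards acute kidney injury as an expected event, and 7.4.3 has a study-level stopping criterion based on creatinine. Section 13.7 would let the DMC open enrolment to subjects with eGFR down to 30 mL/min/1.73 m², who would follow the same fixed step.

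**Working it through.** This is calendar arithmetic; no power or sample-size figure is involved.

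**Inputs from the protocol**
- Increase on Day 15 (synopsis, 7.1, 7.3, 10.3).
- Week 1 = Day 8 ± 1 = Day 7–9; Week 2 = Day 15 ± 1 = Day 14–16; Week 4 = Day 29 ± 1 = Day 28–30 (11.3.4). Week 3 = Day 22 ± 1 = Day 21–23 (11.3.5).
- Dosing at 08:00 and 20:00, the example in 9.3.

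**Assumptions, not in the documents**
- Two doses on Day 1; blood drawn at 10:00.
- Turnaround T of 1 to 3 days, with T = 0 (same-day local result) shown for comparison.

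**Step 1. Age of the Week 1 creatinine on Day 15.** 15 − 9 = 6 days to 15 − 7 = 8 days.

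**Step 2. Lead-in doses not covered by it.** Total at 200 mg = 14 × 2 = 28. Doses taken before a sample on Day d number 2(d − 1) or 2(d − 1) + 1: 12–13 on Day 7, 14–15 on Day 8, 16–17 on Day 9. Doses after the sample run from 28 − 17 = 11 to 28 − 12 = 16, or 39% to 57% of the lead-in. Steps 1 and 2 need no turnaround figure.

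**Step 3. Can the Week 2 result be in hand?** With result day R = V + T, where V is the visit day, the 400 mg doses taken before the result number 2(R − 15) or 2(R − 15) + 1 if R ≥ 15, otherwise 0.

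| Week 2 draw (V) | Turnaround needed before Day 15 08:00 dose | Before Day 15 20:00 dose | 400 mg doses before result, T = 0 | T = 1 to 3 |
|---|---|---|---|---|
| Day 14 | under 22 h | under 34 h | 0 | 0–5 |
| Day 15 | not possible | under 10 h | 0–1 | 2–7 |
| Day 16 | not possible | not possible | 2–3 | 4–9 |

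At a turnaround of 2 days or more, no draw in the window gives a result on Day 15, and Week 1 is the newest scheduled value.

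**Step 4. Effect of waiting for the result.** Delay = max(0, V + T − 15). The smallest is max(0, 14 + 1 − 15) = 0 and the largest is 16 + 3 − 15 = 4 days, so the increase falls on Day 15 to 19.
- Time on 400 mg before the Week 3 sample: step on Day 15 gives 21 − 15 = 6 to 23 − 15 = 8 days; step on Day 19 gives 2 to 4. The range widens from 6–8 to 2–8 days.
- Before the Week 4 sample: step on Day 15 gives 13–15 days; step on Day 19 gives 28 − 19 = 9 to 30 − 19 = 11 days.

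**The case against.** The strongest objection is that the relevant rule may exist but be out of sight. The contents list Section 13.5.2 on monitoring, evaluation and discontinuation for renal events, 5.5.3.4 refers to it, and its text is not in the supplied document. That stands. A reader might infer that the protocol doubles the dose with no renal safeguard; the documents do not support that. What can be said is that the visible dosing statements neither state a check before the increase nor point to one.

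Second, no turnaround is given, so the Week 2 result cannot be called always too late. That also stands. A Day 14 visit with a result in about a day, a same-day result on Day 15 before an evening first 400 mg dose, or an unscheduled test would each supply a newer value.

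Third, investigators review results as they arrive (12.11.5), may interrupt or reduce dosing for possibly drug-related events (10.3.1), and can receive advice from the nephrology working group (5.5, 13.7). Scheduled chemistry is weekly through Week 8. These are genuine protections, but each acts on a result already in hand; none supplies one before the increase.

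Fourth, a fixed step with close follow-up is a legitimate design, and 5.5.5 does not describe a titration conditional on creatinine. Waiting also shortens the time on 400 mg before the Week 3 sample. Both are correct, which is why this is an improvement rather than a defect. Subjects under earlier protocol versions were to receive 500 mg BID, so a few doses at 400 mg are below that regimen. But the sponsor lowered the dose and added the lead-in to reduce renal risk, so the earlier dose does not settle the matter.

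A reader might also suspect that a Week 2 sample is distorted by 400 mg doses already taken. At most one precedes a Day 15 sample and two or three a Day 16 sample, and nothing in the documents shows that this changes creatinine.

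**Conclusion.** The point holds in a limited form. In the visible text the doubling is fixed on Day 15. Unless the Week 2 result returns within about a day, or a local or unscheduled test is used, the newest creatinine is 6 to 8 days old and 11 to 16 of the 28 lead-in doses follow it. The age comes from the protocol's visit windows alone; the dose count also assumes two doses on Day 1. How often the Week 2 result misses the increase depends on a turnaround that the documents do not give.

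This is a cheap improvement to the Version 4.0 plan, not an error. A reader might infer that treated subjects or reported results were affected. They were not: SAP 4.1 states that the programme stopped before anyone enrolled under Version 4.0, so no newly enrolled subject followed the step-up. The point matters for the plan as written and for any reuse of the regimen. The arithmetic counts days and doses; it gives no probability of renal harm. Confidence is medium, mainly because Section 13.5.2 cannot be read.

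**What to change.** In Protocol 7.3, 10.3 and 11.3.4, state that:
1. The Week 2 sample is drawn before the first 400 mg dose.
2. The subject stays on 200 mg BID until the investigator has reviewed the Week 2 creatinine; 400 mg BID starts on Day 15 or after that review, whichever is later.
3. If the central result is late, a local creatinine is used, which 12.11.5 already allows.

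No creatinine threshold is proposed; the response to an abnormal value stays with 7.4.1, 10.3.1 and whatever 13.5.2 contains. If 13.5.2 already requires this review, a cross-reference from 10.3 is enough.

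The cost is wording in three sections, handled as a protocol amendment, and one site contact per subject to release the dose, with an occasional local test. Under the assumed turnaround of 1 to 3 days, the step-up falls on Day 15 to 19. The price is less time on 400 mg before the Week 3 sample, as little as 2 days in the worst case; the Week 4 sample still follows at least 9 days on 400 mg.
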